### **9.3.3 Reporting of serious adverse events**

All SAEs associated with the investigational product will be reported, whether or not considered causally related to the investigational product. The reporting period for SAEs associated with the investigational product is the period immediately following the time that written informed consent is obtained through 90 days after the last dose of MEDI4736 or until the initiation of alternative anticancer therapy. The investigator and/or Sponsor are responsible for informing the Ethics Committee and/or the Regulatory Authority of the SAE associated with the investigational product as per local requirements.

The investigator and/or sponsor must inform the FDA, via a MedWatch/AdEERs form, of any serious or unexpected adverse events associated with the investigational product that occur in accordance with the reporting obligations of 21 CFR 312.32, and will concurrently forward all such reports to AstraZeneca. A copy of the MedWatch/AdEERs report must be faxed to AstraZeneca at the time the event is reported to the FDA. It is the responsibility of the sponsor to compile all necessary information and ensure that the FDA receives a report according to the FDA reporting requirement timelines and to ensure that these reports are also submitted to AstraZeneca at the same time.

\* A *cover page* should accompany the **MedWatch/AdEERs** form indicating the following:

- “Notification from an Investigator Sponsored Study”
- The investigator IND number assigned by the FDA
- The investigator’s name and address
  - The trial name/title and AstraZeneca ISS reference number (ESR-##-#####)

\* Sponsor must also indicate, either in the SAE report or the cover page, the *causality* of events ***in relation to all study medications*** and if the SAE is ***related to disease progression***, as determined by the principal investigator.

\* ***Send SAE report and accompanying cover page by way of email to AstraZeneca's designated mailbox:*** [contact]

If a non-serious AE associated with the investigational product becomes serious, this and other relevant follow-up information must also be provided to AstraZeneca and the FDA.

Serious adverse events associated with the investigational product that do not require expedited reporting to the FDA still need to be reported to AstraZeneca preferably using the MedDRA coding language for serious adverse events. This information should be reported on a monthly basis and under no circumstance less frequently than quarterly.

#### 9.3.3.1 Reporting of deaths

All deaths that occur during the study, or within the protocol-defined 90-day post-last dose of MEDI4736 or tremelimumab safety follow-up period must be reported as follows:

- Death that is clearly the result of disease progression should be documented but should not be reported as an SAE.
- Where death is not due (or not clearly due) to progression of the disease under study, the AE causing the death must be reported to as a SAE within **24 hours** (see Section 10.3.2 for further details). The report should contain a comment regarding the co-involvement of progression of disease, if appropriate, and should assign main and contributory causes of death.
- Deaths with an unknown cause should always be reported as a SAE.

Deaths that occur following the protocol-defined 90-day post-last-dose of MEDI4736 safety follow-up period will be documented as events for survival analysis, but will not be reported as an SAE.

### **9.3.4 Other events requiring reporting**

#### **9.3.4.1 Overdose**

An overdose is defined as a subject receiving a dose of MEDI4736 or tremelimumab in excess of that specified in the Investigator's Brochure, unless otherwise specified in this protocol.

Any overdose of a study subject with MEDI4736 or tremelimumab, with or without associated AEs/SAEs, is required to be reported within 24 hours of knowledge of the event to the sponsor and AstraZeneca/MedImmune Patient Safety or designee using the designated Safety e-mailbox (see Section 10.3.2 for contact information). If the overdose results in an AE, the AE must also be recorded as an AE (see Section 10.3). Overdose does not automatically make an AE serious, but if the consequences of the overdose are serious, for example death or hospitalization, the event is serious and must be recorded and reported as an SAE (see Section 10.1.2 and Section 10.3.2). There is currently no specific treatment in the event of an overdose of MEDI4736 or tremelimumab.

The investigator will use clinical judgment to treat any overdose of MEDI4736 or MEDI4736 + tremelimumab.

#### **9.3.4.2 Hepatic function abnormality**

Hepatic function abnormality (as defined in Section 10.1.3.3) in a study subject, with or without associated clinical manifestations, is required to be reported as "hepatic function abnormal" ***within 24 hours of knowledge of the event*** to the sponsor and AstraZeneca/MedImmune Patient Safety using the designated Safety e-mailbox (see Section 10.3.2 for contact information), unless a definitive underlying diagnosis for the abnormality (e.g., cholelithiasis or bile duct obstruction) that is unrelated to investigational product has been confirmed.

- If the definitive underlying diagnosis for the abnormality has been established and is unrelated to investigational product, the decision to continue dosing of the study subject will be based on the clinical judgment of the investigator.
- If no definitive underlying diagnosis for the abnormality is established, dosing of the study subject must be interrupted immediately. Follow-up investigations and inquiries must be initiated by the investigational site without delay.

Clinical Study Protocol

Drug Substance Tremelimumab

Study Number **ESR-14-10744**

Edition Number 8

Date 17 April 2019

Each reported event of hepatic function abnormality will be followed by the investigator and evaluated by the sponsor and AstraZeneca/MedImmune.

### **9.3.4.3    Pregnancy**

Pregnancy itself, or pregnancy of a subject's partner, is not regarded as an adverse event unless there is a suspicion that the investigational product under study may have interfered with the effectiveness of a contraceptive medication. Congenital abnormalities/birth defects and spontaneous miscarriages should be reported and handled as SAEs. Elective abortions without complications should not be handled as AEs. The outcome of any conception occurring from the date of the first dose until 90 days after the last dose (spontaneous miscarriage, elective termination, ectopic pregnancy, normal birth or congenital abnormality) should be followed up and documented even if the subject was withdrawn from the study.

Pregnancy in a female subject who has received investigational product is required to be reported ***within 24 hours of knowledge of the event*** to the sponsor and AstraZeneca/MedImmune Patient Safety or designee using the designated Safety e-mailbox (see Section 10.3.2 for contact information).

Subjects who become pregnant during the study period must not receive additional doses of investigational product but will not be withdrawn from the study. The pregnancy will be followed for outcome of the mother and child (including any premature terminations) and should be reported to AstraZeneca/MedImmune Patient Safety or designee after outcome.

Male subjects should refrain from fathering a child or donating sperm during the study and for 90 days following the last dose of monotherapy MEDI4736 or for 180 days following the last dose of combination therapy with MEDI4736 and tremelimumab.

Should the investigator become aware of a pregnancy in the partner of a male study subject who has received investigational product this should be reported ***within 24 hours of knowledge of the event*** to AstraZeneca/MedImmune Patient Safety or designee using the Safety Fax Notification Form for contact information). The sponsor will endeavor to collect follow-up information on such pregnancies provided the partner of the study subject provides consent.

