### **Withdrawal of consent**

Patients are free to withdraw their consent to further participation in this trial without prejudice. If consent is withdrawn, the subject will not receive any further investigational product or further study observation.

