### **5.3.2 Procedures for handling subjects incorrectly enrolled or randomized**

Subjects who are incorrectly enrolled in the study but have not yet received treatment with MEDI4736 or MEDI4736 + tremelimumab will be withdrawn from the study and will receive standard of care treatment for their MPM.

Subjects who are found to have been incorrectly enrolled after receiving treatment will be withdrawn from the study and will receive standard of care treatment for their MPM. Such patients will be replaced by eligible subjects with MPM. These subjects also will be followed for 90 days to track any AEs, SAEs, etc. from the treatment. These subjects will not be included in any data analyses.

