## **6. RESTRICTIONS DURING THE STUDY AND CONCOMITANT TREATMENT(S)**

### **6.1 Restrictions during the study**

#### **Contraception**

Female subjects of childbearing potential who are sexually active with a non-sterilized male partner must use at least one highly effective method of contraception (Table 5) from the time of screening and must agree to continue using such precautions for 90 days after the last dose of mono-therapy MEDI4736 or for 180 days after last dose of combination therapy with MEDI4736 and tremelimumab. The male partner of a female subject must also use male condom plus spermicide throughout this period. Cessation of birth control after this point should be discussed with a responsible physician. Not engaging in sexual activity is an acceptable practice; however, occasional abstinence, the rhythm method, and the withdrawal method are not acceptable methods of contraception. Female patients should refrain from breastfeeding and egg cell donation throughout this period.

- Females of childbearing potential are defined as those who are not surgically sterile (i.e., bilateral tubal ligation, bilateral oophorectomy, or complete hysterectomy) or postmenopausal (defined as 12 months with no menses without an alternative medical cause).
- Effective methods (including highly effective methods) of contraception are described in Table 5. A highly effective method of contraception is defined as one that results in a low failure rate (ie, less than 1% per year) when used consistently and correctly. Note that not all methods in Table 1 are considered highly effective.
- Non-sterilized male subjects who are sexually active with a female partner of childbearing potential must use male condom plus spermicide (see Table 5) from screening through 90 days after the last dose of mono-therapy MEDI4736 or for 180 days after last dose of combination therapy with MEDI4736 and tremelimumab. Not engaging in sexual activity is an acceptable practice; however, occasional abstinence, the rhythm method, and the withdrawal method are not acceptable methods of contraception. Male patients should refrain from sperm donation throughout this period. Female partners of a male subject must use an effective method of contraception throughout this period.

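### The duty to document conception outcomes in 9.3.4.3 ends 90 days after the last dose in both treated arms, although the combination carries a 180-day contraception and no-fathering period

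*Combined protocol and SAP*

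**What the plan says.** Section 9.3.4.3 (Pregnancy) sets one outcome window, with no split by arm: "The outcome of any conception occurring from the date of the first dose until 90 days after the last dose". Outcomes in that window, including normal birth, elective termination and ectopic pregnancy, are to be followed and documented, and the sentence expressly reaches subjects who have left the study.

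The precaution periods do differ by arm. In section 6.1 (Contraception) both sexes take precautions for 90 days after monotherapy but "for 180 days after last dose of combination therapy with MEDI4736 and tremelimumab". A later paragraph of 9.3.4.3 tells male subjects not to father a child or donate sperm for 90 days after monotherapy and "for 180 days following the last dose of combination therapy with MEDI4736 and tremelimumab".

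Other provisions of 9.3.4.3 carry no day limit:

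- A pregnancy in a treated female subject, or one in a male subject's partner that the investigator learns of, is reported within 24 hours.
- For a subject who becomes pregnant during the *study period*, a term the protocol does not define: "The pregnancy will be followed for outcome of the mother and child".
- For partners: "The sponsor will endeavor to collect follow-up information on such pregnancies provided the partner of the study subject provides consent".
- "Congenital abnormalities/birth defects and spontaneous miscarriages should be reported and handled as SAEs".

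**The concern.** The protocol treats conception as something to prevent for 180 days after the combination. The one sentence that firmly requires the outcome to be documented stops halfway through that period. A site could follow the sentence exactly and leave undocumented the outcome of a conception on day 120 after the combination, although the protocol sought to prevent that conception.

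Subjects able to conceive or father a child may enrol. Inclusion criterion 5 in section 4.1 admits women with a negative pregnancy test. Exclusion criterion 20 in section 4.2 removes subjects of reproductive potential only if they do not use effective birth control. At stake is completeness of pregnancy safety data in the combination arm, not any endpoint.

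**Working it through.** The plan states no figure to reproduce, so the check compares the stated windows and then reads the other provisions against days 91 to 180.

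**Inputs.** Outcome window: 90 days after last dose, both arms (9.3.4.3). Precaution period: 90 days after monotherapy, 180 days after the combination (6.1, 9.3.4.3). One dose per subject (5.6), so first and last dose coincide. Eight combination subjects (5.3).

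**Shortfall = precaution period - outcome window.**

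- Monotherapy: 90 - 90 = 0 days.
- Combination: 180 - 90 = 90 days; 90 / 180 = one half.

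**What else applies on days 91 to 180 after the combination?**

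1. *Female subject still in the study.* The answer depends on what *study period* means.
   - If it means her own follow-up, section 7.1.3 gives at least 12 months from entry. Counting entry from consent, the latest planned infusion is screening 28 + biopsy 7 + infusion 21 = 56 days later. Day 180 after the dose is then 56 + 180 = day 236, which is 365 - 236 = 129 days inside follow-up. The gap is zero.
   - If it means trial duration, section 12.3 ends the study 90 days after the final subject's infusion. A subject dosed D days before that infusion has D + 90 days of cover, which reaches 180 when D is 90 or more. Only combination subjects dosed less than 90 days before the final infusion lose any cover.

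2. *Partner pregnancy.* The 24-hour report is undated but depends on the investigator becoming aware. Follow-up is undated but worded as an endeavour that needs the partner's consent. There is cover, but no firm duty to document the outcome.

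3. *Withdrawn subject.* The 24-hour report for a treated female subject still applies, since it has no end date and is not limited to subjects in the study. Only the 90-day sentence expressly carries outcome documentation past withdrawal, so no outcome duty clearly applies after day 90.

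4. *Miscarriage or birth defect.* Section 9.3.4.3 handles both as SAEs without an end date, and 9.1.2 lists birth defect in a subject's offspring as an SAE criterion. The SAE reporting period in 9.3.3 ends at 90 days or at the start of other anticancer therapy. Separately, under Post study events in 9.3.1, an investigator who learns at any later time of an SAE in a withdrawn subject, and thinks it may reasonably be related, notifies the sponsor and the drug company. That route cannot capture a normal birth or an uncomplicated elective termination, which 9.3.4.3 says is not an AE.

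**The case against.** The strongest reply is that the rest of the protocol already covers most of days 91 to 180, in a small arm where contraception is mandatory. Much of that stands, and it rules out several stronger readings.

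- *A reader might infer that these 90 days are wholly uncovered.* They are not. Pregnancy reports are undated, and a female subject who stays in the study has no gap if the study period is her own follow-up.
- *A reader might infer that partner pregnancies go unfollowed.* The partner paragraph has no time limit. Only the firm outcome duty is absent, and any firmer duty would still depend on the partner's consent.
- *A reader might infer that a late miscarriage or birth defect is reportable only if the undated SAE sentence overrides the 90-day SAE period.* The Post study events paragraph is a separate route after withdrawal, though it depends on the investigator hearing of the event and judging it possibly related.
- *A reader might infer that treated subjects found to be incorrectly enrolled are dropped at day 90*, because 5.3.2 says "These subjects also will be followed for 90 days to track any AEs, SAEs, etc. from the treatment". That sentence does not say 90 days is all they get. Section 4.3 sends permanently discontinued subjects, including some who met an exclusion criterion at entry, to the safety follow-up section and Appendix B, which has contacts beyond month 6. The two sections sit uneasily together, so this group is not a clean example of a gap.

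Withdrawal of consent is a real limit. Under 4.3, "the subject will not receive any further investigational product or further study observation", so no rewording of the window would permit continued observation of those subjects.

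None of this explains why a section that separates 90 from 180 days for fathering uses 90 days for everyone in its outcome sentence.

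**Conclusion.** The point holds in a narrow form. For the combination arm the outcome sentence covers 90 of the 180 days that the protocol itself treats as the precaution period; for monotherapy it covers all 90. On days 91 to 180 a firm duty to document the outcome is missing for partner pregnancies and for withdrawn subjects.

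This rests on two readings: that any conception in the outcome sentence includes a partner's, and that the undefined study period covers a retained female subject's own follow-up. If the second fails, late-dosed female combination subjects join the gap.

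The 90 days is a window length, not a measure of harm. The documents do not say how many of the 8 subjects, or their partners, could conceive, so no event count can be given. With 8 subjects, one dose each and required contraception, events should be rare. No efficacy analysis, sample size or power figure is affected. It is a minor correction, worth making because it is cheap.

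**What to change.** In the outcome sentence of 9.3.4.3, replace the single 90-day limit with: *until 90 days after the last dose of MEDI4736 monotherapy or 180 days after the last dose of combination therapy*, and add that partner outcomes are subject to the partner's consent.

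The cost is one clause and a short qualifier, reviewed by the sponsor and the IRB as section 11.4 requires for any protocol change. No extra visits, pregnancy questions or telephone calls are needed; the existing sentence prescribes none even within its 90 days. The change cannot compel data from a partner who declines or reach a subject who has withdrawn consent to observation.

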## **10. STATISTICAL METHODS AND SAMPLE SIZE DETERMINATION**

This is a pilot study designed to show that combination therapy with MEDI4736 and tremelimumab can have a substantial impact on surgically resectable MPM patients. All subjects will be randomized after the mediastinoscopy + thoracoscopy to one of the three arms to receive MEDI4736+tremelimumab, MEDI4736 only, or untreated control. The primary endpoint will be the ratio of intratumoral cytotoxic T cells to regulatory T cells (CD8/Treg) before and after treatment. The secondary endpoints are the percentage of inducible T-cell co-stimulator (ICOS) positive intratumoral CD4 T cells and tumor tissue expression (Ventana assay) of programmed death-ligand 1 (PD-L1) before and after each treatment. Overall and recurrence-free survival will be also measured as the secondary endpoint. These analysis will be post-protocol analysis based upon data obtained from the standard of care follow up in our post-surgical patients. All subjects will undergo surgical resection One to six weeks after the infusion.

### **10.1 Sample size**

**10.2** The primary objective is comparison of the ratio of CD8/Treg before and after treatment with combination MEDI4736+Tremelimumab. A total of 20 evaluable subjects (if tissue obtained) will be enrolled in this study for 24 months and 8 subjects will be assigned to combination MEDI4736+Tremelimumab (8 subjects to MEDI4736 only and 4 subjects to control). The outcome of interest in this study is a change in ratio of CD8/Treg before and after treatment with combination MEDI4736+Tremelimumab within subjects. There are no data available to estimate a change of ratio of CD8/Treg before and after the treatment but in our pilot data from 6 subjects with MPM the log transformed ratio of CD8/Treg was approximately normally distributed with a mean of 1.94(6.96 in raw scale) and standard deviation of 0.808(2.24 in raw scale). Assuming that repeat values are moderately correlated( $r=0.5$ ), then the difference between before and after the combination treatment will also have a standard deviation of 0.808(2.24 in raw scale). We estimate that we will have 80% power ( $\alpha=5\%$ , a paired t-test) to detect an increased log ratio CD8/Treg of 2.87(17.71 in raw scale) after the combination treatment with 8 subjects.

### **10.3 Analysis plan**

There will be two treatment arms (MEDI4736 only and combination MEDI4736+tremelimumab) and one untreated arm (control). Randomization, stratified by receiving previous chemotherapy or not, will help to minimize patient selection biases between three arms. Preliminary tests will be performed to assess whether our data is normally or non-normally distributed. Patient characteristics will be summarized descriptively. Baseline characteristics will be compared by treatment assignment. For our primary objective that compares outcome variable in tissues before and after treatment with combination MEDI4736

Clinical Study Protocol

Drug Substance Tremelimumab

Study Number **ESR-14-10744**

Edition Number 8

Date 17 April 2019

and tremelimumab, we will use a paired t-test in log-transformed ratio of intratumoral cytotoxic T cells to regulatory T cells (CD8/Treg) before and after the treatment. In our secondary objective numerous variable comparisons are made between tumor tissues from untreated patients with from patients undergoing treatment with either MEDI4736 or MEDI4736 + tremelimumab, and between tumor tissues from patients undergoing treatment with MEDI4736 and tumor tissues from patients undergoing treatment with MEDI4736+tremelimumab. In these comparisons, a paired t-test or Student t-tests will be performed. Because approximately 20 comparisons of immune cell populations will be performed, a Bonferroni correction will be applied to correct for multiple comparisons. For the comparison of overall survival and recurrence-free survival between treatment groups, log-rank test will be used. These analysis will be post-protocol analysis based upon data obtained from the standard of care follow up in our post-surgical patients. SAS software will be used for all other statistical analyses.

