### **2.2 Secondary objective(s)**

The secondary objectives of this study are:

- 1) Comparison of the percentage of inducible T-cell co-stimulator (ICOS) positive intratumoral CD4 T cells before and after treatment with combination MEDI-4736 and Tremelimumab checkpoint inhibitor therapy.
- 2) Comparison of tumor tissue expression (Ventana assay) of programmed death-ligand 1 (PD-L1) before and after treatment with combination MEDI-4736 and Tremelimumab checkpoint inhibitor therapy.
- 3) Comparison of the ratio of the intratumoral CD8/Treg ratio in patients treated with combination therapy (MEDI-4736 and Tremelimumab) compared to either patients treated with MEDI-4736 alone, and separately compare to untreated patients.
- 4) Comparison of the percentage of inducible T-cell co-stimulator (ICOS) positive intratumoral CD4 T cells in patients treated with combination therapy (MEDI-4736 and Tremelimumab) compared to either patients treated with MEDI-4736 alone, and separately compare to untreated patients.

- 5) Comparison of tumor tissue expression (Ventana assay) of programmed death-ligand 1 (PD-L1) in patients treated with combination therapy (MEDI-4736 and Tremelimumab) compared to either patients treated with MEDI-4736 alone, and separately compare to untreated patients. These analysis will be post-protocol analysis based upon data obtained from the standard of care follow up in our post-surgical patients.
- 6) Comparison of overall survival in patients treated with either MEDI-4736 alone or MEDI-4736 plus Tremelimumab with historical untreated controls. These analysis will be post-protocol analysis based upon data obtained from the standard of care follow up in our post-surgical patients.
- 7) Comparison of recurrence-free survival in patients treated with either MEDI-4736 alone or MEDI-4736 plus Tremelimumab with historical untreated controls. These analysis will be post-protocol analysis based upon data obtained from the standard of care follow up in our post-surgical patients.

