## **TREATMENT PLAN**

### **5.3 Subject enrollment and randomization**

We expect to enroll a total of 20 evaluable subjects (if tissue obtained at time of thoracoscopy and time of surgical resection) with surgically resectable MPM to this study over a period of 24 months. Subjects will be randomized. Subjects will be assigned to one of the three treatments (n = 8 MEDI4736, n = 8 MEDI4736 + tremelimumab, and n=4 control). All subjects will undergo surgical resection one to six weeks after the infusion.

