#### **5.3.1 Procedures for randomization**

After mediastinoscopy + thoracoscopy, eligible subjects with MPM will be randomized in 2:2:1 ratio to one of three arms: MEDI4736 alone, MEDI4736 + tremelimumab, and a control group of neither MEDI4736 nor tremelimumab. A computer-generated randomization scheme may be generated by the Biostatistics Core, Baylor College of Medicine. Randomization will be accomplished via access to a secure website developed by the Biostatistics Core and automatically notified to the study coordinator or the investigator via email. Randomization will be stratified by receiving previous chemotherapy or not.

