8) Additional tissue biomarker immune response to MEDI4736 or MEDI4736 + tremelimumab determined with CyTOF. A comprehensive evaluation of immune cell composition and phenotype will be compared between preoperative and postoperative tumor tissue and peripheral blood. Appendix C details the complete CyTOF panel that will be used for each individual specimen. Substudies will include:

- a. Changes in T-cell subset (CD4, CD8, FoxP3) frequency and memory and activation phenotype (CD25, CD127, CD45RA, CD62L, CCR4, CCR6, Tim1)
- b. Changes in T-cell polarization state (intracellular interferon-gamma, TNF-alpha, IL-17, IL-2)
- c. Changes in myeloid cell composition: dendritic cells, macrophage, MDSC, neutrophil (HLA-DR, CD11c, BDCA-1, BDCA-2, BDCA-3, BDCA-4, CD68, CD163, CD206, CD66b, CD15)
- d. Changes in NK cell and NK T-cell composition (CD56, CD3, V224, Vbeta11)

9) Bone marrow biomarker immune response to MEDI4736 or MEDI4736 + tremelimumab. CyTOF will be used to compare immune cell composition and phenotype, as outlined above in number 8, in the bone marrow (from a routinely resected sixth rib) from patients treated with MEDI4736 or MEDI4736 + tremelimumab, and untreated controls.

3) Tumor and peripheral blood immune cell expression of PD-1 and CTLA-4

- a. CyTOF will be used to compare PD-1 and CTLA-4 expression on specific immune cell and non-immune cell populations.

4) Tissue immune gene expression in response to MEDI4736 or MEDI4736 + tremelimumab

- a. NanoString gene expression arrays will be used to compare gene expression of 300 immune-related genes in tumor tissue obtained preoperatively and postoperatively

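### Randomisation is stratified by prior chemotherapy, but no between-arm analysis uses the stratum; if prior chemotherapy affects the immune read-outs, intervals are too wide and power is lost.

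*Combined protocol and SAP*

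**What the plan says.** Section 5.3.1 states that "eligible subjects with MPM will be randomized in 2:2:1 ratio to one of three arms" and that "Randomization will be stratified by receiving previous chemotherapy or not". Section 5.3 gives the arm sizes: "n = 8 MEDI4736, n = 8 MEDI4736 + tremelimumab, and n=4 control". The synopsis, section 3.1 and section 10.3 repeat the stratification; section 10.3 gives its purpose: "Randomization, stratified by receiving previous chemotherapy or not, will help to minimize patient selection biases between three arms".

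The analysis text appears in the synopsis (Statistical Methods and Data Analysis) and in section 10.3. For comparisons between treated and untreated tumours, and between the two treated arms, it says: "In these comparisons, a paired t-test or Student t-tests will be performed". For survival it says: "For the comparison of overall survival and recurrence-free survival between treatment groups, log-rank test will be used". No test is described as stratified or adjusted, and no covariate model is given. Baseline characteristics are to be compared by arm, but that is description and not adjustment.

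The comparisons concerned are secondary objectives 3 to 5 in section 2.2 (CD8/Treg, ICOS+ CD4 and PD-L1, combination against MEDI4736 alone and against untreated), the immune-cell comparisons in section 10.3, and item 9 of section 8.1.2, which compares immune cells "in the bone marrow (from a routinely resected sixth rib) from patients treated with MEDI4736 or MEDI4736 + tremelimumab, and untreated controls".

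**The concern.** Balancing the arms on a factor makes the difference in means less variable if the factor is prognostic. A pooled two-sample t-test does not register that gain, because it counts the spread between strata as noise. The reported interval is then wider than the design warrants, and the true type I error falls below the nominal level. The design effort of stratifying is spent and its benefit is not collected.

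With arms of 8, 8 and 4 there is little precision to give away. The bone-marrow comparisons are the most exposed. Section 7.3.1 takes marrow only from the rib removed at resection, so there is no pre-treatment value to adjust for, and the stratum is the planned design covariate available.

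**Working it through.** **The plan's own figure.** Section 10 (Sample size) gives a mean log CD8/Treg of 1.94, SD 0.808, correlation 0.5 (so the SD of the change is also 0.808), and a detectable post-treatment mean of 2.87 with 8 subjects at 80% power. The change is 2.87 − 1.94 = 0.93. The noncentrality is 0.93/0.808 × √8 = 3.26 on 7 df, and the two-sided 5% exact power is 79.7%. The stated 80% reproduces. It concerns a within-patient test in one arm, so the stratum does not enter it. The documents give no power for any between-arm test.

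**Inputs for the between-arm check.** Residual SD 0.808 and arm difference 0.93 (both borrowed from the sample size section), arm sizes 8/8/4 (section 5.3), one binary stratum. Two assumptions are not in the documents: the shift *g* due to prior chemotherapy, and an even split of the strata within every arm.

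**How much the standard error is inflated.** With N subjects in two arms and the strata balanced at one half, the unadjusted pooled variance has expectation σ² + N × ¼ × g²/(N − 2). At g = 0.808, σ² = 0.653:

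- 8 v 8: 0.653 + 16 × 0.25 × 0.653/14 = 0.839, a ratio of 1.29, so the standard error is about √1.29 = 1.13 times too large.
- 8 v 4: 0.653 + 12 × 0.25 × 0.653/10 = 0.849, a ratio of 1.30, or about 1.14 times.

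**Simulated power.** Two-sided 5% level, difference 0.93, two-sample t-test against a two-arm linear model with the stratum:

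| Shift g | 8 v 8, t-test | 8 v 8, with stratum | 8 v 4, t-test | 8 v 4, with stratum |
|---|---|---|---|---|
| 0 | 57% | 57% | 40% | 39% |
| 0.5 | 53% | 57% | 36% | 39% |
| 0.808 | 47% | 57% | 30% | 39% |

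Under no treatment difference at g = 0.808, the t-test rejects in about 2.8% of runs and the adjusted model in about 5%.

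**Reading 0.808 as the total SD instead.** The pilot SD may already contain stratum variation. Let R² be the share of outcome variance due to prior chemotherapy, with the total SD held at 0.808:

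| R² | Type I error of t-test (8 v 8) | Power 8 v 8, t-test → adjusted | Power 8 v 4, t-test → adjusted |
|---|---|---|---|
| 0.1 | 3.9% | 57% → 61% | 38% → 42% |
| 0.3 | 1.9% | 56% → 72% | 35% → 52% |
| 0.5 | 0.5% | 55% → 85% | 31% → 66% |

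At R² = 0.3 the mean 95% interval narrows from 1.74 to 1.43 (8 v 8) and from 2.22 to 1.82 (8 v 4), about 18% in each case. Judged by interval width, the stratum pays for its lost degree of freedom once R² exceeds about 1.4% (8 v 8) or 3% (8 v 4).

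**The three-arm model.** Fitting all 20 subjects with three arm means and the stratum leaves 20 − 4 = 16 residual df, against 14 and 10 for the separate t-tests. At g = 0.808 its power is 58% (8 v 8) and 42% (8 v 4). At g = 0 it is also 58% and 42%, so nothing is lost even if prior chemotherapy is irrelevant. This assumes a common variance across arms, which Student's t-test already assumes for each pair.

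**The case against.** Several points on the other side are fair.

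- **The primary analysis is untouched, and the error is conservative.** Both are true. What is affected is secondary or exploratory in a trial that section 10 calls a pilot. That limits the severity but does not make the analysis match the design.
- **The documents never say that prior chemotherapy shifts these read-outs.** Also true: the stated motive is avoiding selection bias, and the loss is conditional on a shift. Near zero it is negligible.
- **Conservatism needs realised balance.** Section 5.3.1 gives no block size, and the replacement rule in section 4.4 does not mention the stratum. With a 5/8 v 3/8 split and a one-SD shift, the t-test's type I error is about 4.9%. But the arm difference then carries a bias of 0.808 × (5/8 − 3/8) = 0.20 log units in that allocation, which is another reason to adjust.
- **Bonferroni over about 20 comparisons limits power more.** At 0.05/20 = 0.0025 and a one-SD shift, power is 8% against 14% (8 v 8) and 3% against 6% (8 v 4). The immune-cell tests stay weak after the fix, although their intervals improve.
- **Tumour and blood have pre-treatment samples** (section 7.3). If the stratum shift is the same before and after treatment, adjusting for baseline alone gives 66–67% (8 v 8), and the stratum then adds only 0 to 3 points. A constant shift would also cancel from change scores. However, section 3.1 describes the group comparisons as made after treatment, section 10.3 plans no baseline adjustment, and marrow has no baseline.
- **Survival.** Section 2.2 sets "Comparison of overall survival in patients treated with either MEDI-4736 alone or MEDI-4736 plus Tremelimumab with historical untreated controls" as the objective, and stratified randomisation has no bearing on a historical comparison. The point reaches the log-rank test only if it is run between the randomised arms, as section 10.3 words it.

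**Conclusion.** The concern holds. The trial randomises within prior-chemotherapy strata and plans no between-arm analysis that uses them. If prior chemotherapy matters, the t-tests are conservative and their intervals too wide. Under an assumed one-SD shift with even strata, that costs about 10 points of power for combination against MEDI4736 alone and about 9 points against untreated. At 0.5 log units it costs 3 to 4 points, and if the factor is irrelevant there is no meaningful loss to recover. Treating 0.808 as the total SD makes the gain from adjustment larger at a comparable shift. The size rests on a stratum effect that the documents do not give, and on SD and difference values borrowed from the CD8/Treg sample size calculation. The primary paired test and its 80% power stand. This should be corrected, as a simple improvement to the secondary analyses.

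**What to change.** In section 10.3 and the matching synopsis text, replace the separate Student t-tests for CD8/Treg (log scale), ICOS+ CD4, immune-cell and bone-marrow comparisons with one linear model per variable: arm at three levels plus the prior-chemotherapy stratum as randomised. Take the contrasts of combination against MEDI4736 alone, combination against untreated, and any other planned pair from that model.

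Two additions are worth making in the same edit. Include the pre-treatment value for tumour and blood variables, where one exists. State how PD-L1 will be handled, for example by the same model or by a rank test stratified by prior chemotherapy if the scores are far from normal. If survival is compared between the randomised arms, use a stratified log-rank test.

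The cost is SAP wording, with no extra patients, samples or assays. The stratum uses one degree of freedom, which pooling the three arms more than returns (16 against 14 or 10). The model should be fixed before the data are analysed, so that the adjustment is not chosen after seeing results.
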